## 4 INVESTIGATIONAL PLAN

### STUDY DESIGN AND DURATION

#### Enroll n=45 (15/group) for evaluable n=36 (12/group)

#### **+/- 6 day window for visits**

\*Assessed at week 0, 8 and 16: Primary, Secondary & Tertiary Outcomes.

Week 20: A telephone call to subjects will be made 4 weeks after last dose of study medication to determine if there have been any adverse events.

## 5 STUDY POPULATION

### **Inclusion Criteria:**

1. Able to understand the study, and provide a signed & dated informed consent.
2. Diagnosis of Type 2 diabetes mellitus using criteria of the American Diabetes Association.
3. 30-70 years old.
4. HbA1C 7 to 10%, both inclusive
5. BMI of 25 - 39.9 kg/m^2 both inclusive.
6. Taking a stable dose (for 12 weeks) of Metformin (any dosage), Insulin (any dosage), sulfanylureas ( any dose) or meglitinide ( any dose) for the treatment of T2DM
7. Patients with current Cardiovascular Disease (CVD) in type 2 diabetes patients, defined by  $\geq 1$  of the following:
  - a. MI >2 months prior
  - b. Multivessel CAD
  - c. Angina (intermittent or chronic)
  - d. Single vessel CAD with positive stress test or UA hospitalization in prior year
  - e. UA >2 months prior and evidence of CAD
  - f. Stroke >2 months prior
  - g. Occlusive PAD
  - h. Proteinuria of more than 30mg/dl

### **Exclusion Criteria:**

#### *Past Medical History*

1. Planned CV surgery or angioplasty in 1 month
2. Prior surgery with chronic malabsorption (eg, bariatric) in prior 1 year
3. Diagnosis of Type 1 diabetes mellitus
4. History of GAD antibody positive status
5. Uncontrolled Inflammatory Disease/Inflammatory drug use. *\*\*Evaluated by PI on case-by-case basis\*\**
6. Recent history of diabetic keto-acidosis in the past 3months, or recurrent history of diabetic ketoacidosis ( $\geq 3$  times)
7. Active bladder cancer
8. Active wounds (e.g. Diabetic ulcers) or recent surgery within 1 month
9. Untreated hyper/hypothyroidism
10. Women of child bearing potential who are not willing to use a contraceptive method to avoid pregnancy for the 16 weeks of study duration
11. Women who are pregnant or breastfeeding
12. Implanted devices (eg. Pacemaker) that may interact with Tanita scale
13. Any other clinical condition that would jeopardize patients safety while participating in this clinical trial

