**Protocol Version: Version 1.1**

**May 06, 2019**

**Sponsor: The George Washington University Medical Faculty Associates**

**Funding Source: Astra Zeneca Pharmaceuticals, LP**

## PROTOCOL SYNOPSIS

Protocol Title:	Cardio-Protective Effect of Saxagliptin and Dapagliflozin Combination on Endothelial Progenitor Cells in Patients with Type 2 Diabetes
Site Numbers & Names	GWU Medical Faculty Associates
Research Hypothesis:	We hypothesize that Dapagliflozin will improve EPC number and function AND Saxagliptin in addition to Dapagliflozin (additive effect) may improve EPC number and function even more than Dapa alone, compared to placebo.
Study Schema: Drugs / Doses / Length of Treatment	
We propose a 3-arm randomized, parallel group, longitudinal study of 16-week intervention duration. Patients will be randomized to 3 groups:
 
Group A: Dapa (10 mg) + Saxa Placebo, Enroll n=15, retain n=12  Group B: Dapa (10 mg) + Saxa (5 mg), Enroll n=15, retain n=12  Group C: Dapa Placebo + Saxa Placebo, Enroll n=15, retain n=12
 
Total enroll 45, retain total 36

Study Objectives: 
 
• Primary
 
• Secondary
 
• Tertiary
 
	
Primary Outcome: Cellular Biomarker of Endothelium  The primary objective is to ascertain if 16 weeks of Dapa or Dapa+Saxa Combo therapy will improve CD34+ cell number, function and gene expression in type 2 diabetes with CVD.
 
Secondary Outcome: Arterial Stiffness and Renal Function, Non-Cellular Markers of Endothelium  The secondary objective is to determine whether use of Dapa or Dapa+Saxa Combo alters markers of endothelial function such as: arterial stiffness, blood biochemical measures pertaining to endothelial, renal function, and urine exosomes.
 
Tertiary Outcome: Metabolism Markers  The tertiary objective is to determine whether use of Dapa or Dapa+Saxa Combo alters body composition, fasting lipid profile, and levels of insulin, glucose, and appetite controlling hormones.

Study Design:	Prospective, double-blind, randomized placebo-controlled trial
Accrual Goal (Total number of subjects):	N = 45
Accrual Rate (Number of subjects expected per month):	Recruit 45 patients in approximately 20 months
Estimated Timeline:	FPPV: 06/01/2018 LPLV: 02/28/2020
Co-relative studies (PK/PD, etc.):	N/A

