- Is an important medical event that may jeopardize the subject or may require medical intervention to prevent one of the outcomes listed above. Examples of such events include but are not limited to intensive treatment in an emergency department or at home for allergic bronchospasm; blood dyscrasias or convulsions that do not result in hospitalization. Potential drug induced liver injury (DILI) is also considered an important medical event (see Section 7.6 for the definition of potential DILI)
- Suspected transmission of an infectious agent (e.g., any organism, virus or infectious particle, pathogenic or non-pathogenic) via the study drug is an SAE.
- Pregnancy, only where there is a suspicion that the investigational medicinal product may have interfered with the effectiveness of the contraceptive medication.
- Congenital abnormalities/ birth defects and spontaneous miscarriages.

**NOTE:** The following hospitalizations are **not** considered SAEs:

- A visit to the emergency room or other hospital department lasting less than 24 hours that does not result in admission (unless considered an “important medical event” or a life-threatening event)
- Elective surgery planned before signing consent
- admissions as per protocol for a planned medical/surgical procedure

- Routine health assessment requiring admission for baseline/trending of health status (e.g., routine colonoscopy)
- Medical/surgical admission for purpose other than remedying ill health state that was planned before study entry. Appropriate documentation is required in these cases.
- Admission encountered for another life circumstance that carries no bearing on health status and requires no medical/surgical intervention (e.g., lack of housing, economic inadequacy, caregiver respite, family circumstances, administrative).

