#### **Study Design Overview:**

We propose a 3-arm randomized, double-blind, placebo-controlled, parallel group, longitudinal study of 16-weeks duration. (See study design below), recruited over 20 months. Patients will be randomized to one of 3 groups:

Group A: **Dapa (10 mg)** + matched placebo for Saxa, Enroll n=15, retain n=10

Group B: **Dapa (10) + Saxa (5mg)**, Enroll n=15, retain n=10

Group C: matched **placebo** for Dapa + matched **placebo** for Saxa, Enroll n=15, retain n=10

This proposed study is based on patients with type 2 diabetes and VD, who are taking metformin and/or insulin for anti-diabetic treatment (See section 5 for full inclusion/exclusion criteria).

Though our study is over 16 weeks, we do not anticipate significant drop in HbA1C in between the three groups in this relatively short time period to act as a confounding factor on CD34+ cell number, function and gene expression.

Subjects will be taking 10 mg of Dapa, Dapa+Saxa combo (10 mg Dapa and 5 mg Saxa), or placebo. Dose titration of metformin, will not be allowed. Dose titration of insulin will be allowed to avoid hypoglycemia while maintaining HbA1C under 10%, preferably below 7% as that is the treatment guideline as per ADA. If the subject is only on metformin, Insulin will be started if the patient's glycemic control warrants it, as it can be titrated while the patient is on the study medications.

Visits 1, 2, and 3 with outcome measurements will be scheduled for the morning while overnight fasting (except water) to reduce diurnal variability, and clinical parameters will be obtained at scheduled office visits as depicted in the study schema and will be measured at each outcome visit as follows:

**Before Week -2 (Pre-screening):** Subjects will be pre-screened in person or over the phone to determine initial eligibility. If the pre-screening indicates possible eligibility, then the subjects will come to an in-person screening visit when next available.

**Week -2 (In-person screening):** Subjects will be screened and eligibility will be verified based on physical and laboratory tests. Equal numbers of male and female patients will be recruited.

**Week 0 (Visit 1):** At this stage patients will be randomized into the study. Subjects will have the first set of measurements. We will make sure that patients still meet the inclusion criteria. They will be started on one of the three study arms.

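### Exclusion 1 looks one month ahead from no stated start, so a vascular procedure already booked for later in the 16-week treatment period can fall before the week 8 or week 16 measurements

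*Combined protocol and SAP*

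**What the plan says.** **The criterion.** Section 5, exclusion 1 bars "Planned CV surgery or angioplasty in 1 month". It does not say whether the month runs from consent, screening or randomization.

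**The time frame.** The Synopsis describes a "longitudinal study of 16-week intervention duration", and the Study Design Overview in Section 8 a "longitudinal study of 16-weeks duration". Section 4 gives the measurement times: "Assessed at week 0, 8 and 16: Primary, Secondary & Tertiary Outcomes", with a plus or minus "6 day window for visits".

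**When eligibility is checked.** At week -2, "Subjects will be screened and eligibility will be verified based on physical and laboratory tests". The week 0 re-check in the Study Design Overview mentions only the inclusion criteria.

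**Neighbouring rules.**
- Exclusion 8, "Active wounds (e.g. Diabetic ulcers) or recent surgery within 1 month", looks back for surgery, not ahead.
- Exclusion 13 is a catch-all limited to patient safety.
- Exclusion 10, on contraception, is written for the full 16 weeks.
- The note in Section 7 on hospitalizations that are not SAEs lists "Elective surgery planned before signing consent".
- The discontinuation rules in Section 6 do not mention procedures.
- Section 9 (Data Analysis) adjusts for pre-treatment variables only and has no rule for measurements taken after a procedure.

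**The concern.** Inclusion 7 requires current cardiovascular disease. Several of its qualifying items are conditions for which revascularization may already be scheduled at entry: multivessel coronary disease, angina, single-vessel disease with a positive stress test, and occlusive peripheral disease. The forward-looking exclusion covers only the first part of the period over which outcomes are compared.

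The outcome at stake is the primary one. The Preliminary Results in Section 1 describe the SDF-1/CXCR-4 pathway as important for bringing progenitor cells to ischemic tissue, and speak of these cells homing to damaged endothelium. A revascularization acts on the ischemia and on the vessel wall. The Introduction adds that CD34+ gene expression, which is part of the primary objective, changed within two weeks of an exercise intervention. A procedure shortly before week 8 could therefore plausibly register at that visit. Such a disturbance would enter the group-by-time contrast, which Section 9 names as being of primary interest, in arms of about 12 evaluable patients.

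**Working it through.** The plan gives no figure of its own on this point, so the check compares the exclusion window with the visit schedule.

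**Inputs.** Treatment is 16 × 7 = 112 days. Visits fall on days 0, 56 and 112, and screening on day -14. One month is taken as 30 days, with 28 to 31 as the range. The evaluable number is 36, or 12 per arm (Synopsis and Section 4; the Study Design Overview says 10 per arm).

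**Days left open.** Cover ends at start day + 30.

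| Month starts at | Cover ends | Before both visits | Before week 16 only | Open in total |
|---|---|---|---|---|
| Week 0 | day 0 + 30 = 30 | days 30–56 (26 days) | days 56–112 (56 days) | 82/112 = 73% |
| Week -2 | day -14 + 30 = 16 | days 16–56 (40 days) | days 56–112 (56 days) | 96/112 = 86% |

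With a month of 28 to 31 days the totals are 72–75% and 85–88%. The visit window puts week 8 between days 50 and 62, so the span before both visits is 20 to 32 days (start at week 0) or 34 to 46 days (start at week -2).

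**How often.** The documents give no rate, so the per-patient rates r below are assumptions. Expected cases are 36r. The chance of at least one is 1 − (1 − r)^36. The chance that the counts are not all equal across three arms of 12 is 1 − Σ p(k)³, where p(k) is the binomial(12, r) probability of k cases.

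| Assumed r | Expected cases | At least one | Unequal counts |
|---|---|---|---|
| 2% | 0.7 | 52% | 51% |
| 5% | 1.8 | 84% | 80% |
| 10% | 3.6 | 98% | 91% |

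**How much.** The documents give no effect size either. If, as an assumption, one patient in an arm of 12 is shifted by 3 SD, the arm mean moves by 3/12 = 0.25 SD. The standard error of that mean is 1/√12 = 0.29 SD.

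**The case against.** The strongest reply is that the consequence is small and unquantified.

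- **No bias.** A procedure booked before entry is independent of a blinded random assignment. A reader might infer that the treatment comparison is biased. The documents do not support that; what remains is variance and chance imbalance. This stands.
- **Calendar time is not risk.** A reader might take 73–86% as the share of patients or of risk exposed. It is neither. If exclusion 8's one-month look-back is used as the yardstick for each post-baseline visit, the exposed days are (26 + 30)/112 = 50% counted from randomization, or (30 + 30)/112 = 54% counted from screening. That yardstick ignores lasting effects, but it shows that the percentage depends on a choice the plan does not make. This stands.
- **Not every patient is a candidate.** One item of inclusion 7 is enough, and stroke or proteinuria alone qualifies. This stands.
- **Mechanism.** A reader might infer that a procedure would dominate the measured change, or that wound repair mobilizes CD34+ cells. The plan says neither. It links the cells to ischemic tissue and damaged endothelium, and gives no size or direction for a revascularization effect.
- **Safety reporting.** A reader might infer that such procedures would go unseen. The Section 7 note says only that the admission is not itself an SAE. AE collection and visit assessments continue, so a procedure may still come to light. What is missing is a rule to record it and to handle later measurements.

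None of this closes the window. Exclusions 8 and 13, the discontinuation rules and the analysis section all leave it open. A one-month limit chosen for safety would not protect the outcome measurements.

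**Conclusion.** The point holds as a cheap improvement, not as an error that undermines the design. The one-month limit and the 16-week schedule do not contradict each other; the limit is shorter than the period it would need to protect, and its start is undefined. Only procedures before week 8 precede both post-baseline visits: about days 30–56 or 16–56, depending on the start. A reader might infer that every procedure after the first month affects both visits, but one in week 12, for example, affects week 16 only.

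The expected harm is added variance and chance imbalance in the group-by-time contrast. The durations are certain. The effect on the results cannot be sized from the documents, and the rates and the 3 SD shift used above are illustrations.

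**What to change.** 1. **Eligibility.** Reconcile exclusion 1 with the visit schedule: state when the window starts and extend it to the week 16 visit (Visit 3). No care should be postponed for the trial. A patient with a scheduled procedure can be considered for screening afterwards, subject to exclusion 8.
2. **Recording.** Record the date and type of any vascular procedure, planned or unplanned, between Visits 1 and 3. The eligibility change cannot reach unplanned procedures, which raise the same measurement question.
3. **Analysis.** In Section 9, prespecify a sensitivity analysis that omits measurements taken after such a procedure. It should supplement the primary analysis, not replace it, because an unplanned procedure, unlike one booked before entry, need not be independent of treatment.

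The cost is a one-line amendment, one data field and a sentence in the analysis section, with a few patients excluded or enrolled later. One limit remains: a patient who enters just over a month after surgery may still be recovering between baseline and week 8. Recording the date of recent surgery at entry would let the analysis examine this.

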### **METHOD OF ASSIGNING SUBJECTS TO A TREATMENT**

Subjects, as per selection criteria below will be randomized to treatments using a permuted block design, developed by the Epidemiology & Biostatistics Research Core. This approach ensures groups will be approximately balanced at any time during the study and at study completion. Randomization will be performed by the MFA IDS Pharmacy staff who never come in contact with subjects.

The recommended dose of Dapagliflozin is 10 mg PO will be given once daily in the Dapa group. The recommended dose of Saxagliptin 5mg along with Dapagliflozin 10 mg (one of each) will be given PO once daily in the Dapa+Saxa Combo group. Saxagliptin should be administered once daily with or without food, at any time of day. Dapa should be administered once daily with food, **in the morning**.

*Because of this, all subjects will be instructed to take their medication once daily in the morning with food, as we will not know which subjects will be in the Dapa, Dapa+Saxa Combo, or placebo group.*

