### **Pregnancy**

If, following initiation of the investigational product, it is subsequently discovered that a study subject is pregnant or may have been pregnant at the time of investigational product exposure, including during at least 6 half-lives after product administration, the investigational product will be permanently discontinued immediately. Protocol-required procedures for study discontinuation and follow-up must be performed on the subject unless contraindicated by pregnancy (e.g., x-ray studies). Other appropriate pregnancy follow-up procedures should be considered if indicated.

If any pregnancy occurs in the course of the study, then the Investigator or other site personnel should inform the appropriate AstraZeneca representatives within 1 day, i.e., immediately, but **no later than 24 hours** of when he or she becomes aware of it.

Following initial AstraZeneca notification, the PI will ensure that all relevant information is provided to the AstraZeneca Patient Safety data entry site within 1 to 5 calendar days for SAEs and within 30 days all non SAE pregnancies.

The same timelines apply when outcome information is available.

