### **Serious Adverse Event Collecting and Reporting**

Following the subject's written consent to participate in the study, all SAEs, whether related or not related to study drug, will be collected, including those thought to be associated with protocol-specified procedures. All SAEs will be collected that occur within 30 days of discontinuation of dosing or within 30 days of the last visit for screen failures. If applicable, SAEs will be collected that relate to any later protocol-specified procedure (e.g., a follow-up skin biopsy). The investigator will report any SAE occurring after these time periods that is believed to be related to study drug or protocol-specified procedure at 90 days and 180 days period. An SAE report will be completed for any event where doubt exists regarding its status of seriousness.

The following variables (if applicable) are recommended to be collected for SAEs: date AE met criteria for SAE, date PI became aware of SAE, seriousness criteria fulfilled, date of hospitalization, date of discharge, probable cause of death, date of death, whether an autopsy was performed, causality assessment in relation to study procedures, causality assessment in relation to other study medication, and description of SAE.

If the investigator believes that an SAE is not related to study drug, but is potentially related to the conditions of the study (such as withdrawal of previous therapy, or a complication of a study procedure), the relationship will be specified in the narrative section of the SAE Report Form. All SAEs, whether related or unrelated to Dapa or Saxagliptin, and all pregnancies will be reported to AZ (by the investigator or designee) **within 24 hours**.

The investigator must inform the FDA, via a MedWatch form, of any serious or unexpected adverse events that occur in accordance with the reporting obligations of 21 CFR 312.32, **and will concurrently forward all such reports to AstraZeneca**. A copy of the MedWatch report must be emailed to AstraZeneca (TCS vendor) at the time the event is reported to the FDA. It is

the **responsibility of the Investigator** to compile all necessary information and ensure that the FDA receives a report according to the FDA reporting requirement timelines and to ensure that these reports are also submitted to AstraZeneca at the same time.

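### Exclusion 10 fixes contraception at 16 weeks, the same length as planned dosing, and so leaves little or no cover after the last dose

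*Combined protocol and SAP*

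**What the plan says.** Section 5, Exclusion Criteria, item 10 excludes women of child-bearing potential who are "not willing to use a contraceptive method to avoid pregnancy for the 16 weeks of study duration".

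The same 16 weeks describe treatment. The Protocol Synopsis proposes a "longitudinal study of 16-week intervention duration". The Study Design Overview in section 8 calls the trial a "longitudinal study of 16-weeks duration" and says of participants at week 0 that "They will be started on one of the three study arms". Section 6, on assigning subjects to treatment, says "all subjects will be instructed to take their medication once daily in the morning with food". Section 4 describes the week-20 contact in these words: "A telephone call to subjects will be made 4 weeks after last dose of study medication".

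The Pregnancy part of section 7 tells the site what to do when a participant is found to be pregnant, or to have been pregnant while exposed to the product. It extends that exposure past dosing, "including during at least 6 half-lives after product administration".

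No other part of the supplied text requires contraception after dosing. The discontinuation rules in section 6 ask participants to report a suspected pregnancy, and Appendix C lists a urine pregnancy test as needed.

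**The concern.** Contraception is set as a fixed calendar period that is not tied to the last dose. Because that period equals the planned length of dosing, the two end at about the same time. A woman could meet the requirement in full, take her final tablet at about week 16, stop contraception, and conceive within the interval that section 7 still counts as exposure.

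The protocol's other measures would pick this up afterwards but would not prevent it. These are self-report of a suspected pregnancy, the week-20 call, reporting of pregnancies to the company within 24 hours, and the rule that "All SAEs will be collected that occur within 30 days of discontinuation of dosing". What is at stake is a short, avoidable period of possible fetal exposure in a small number of women.

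**Working it through.** The plan states no figure for post-dose cover, so there is none to reproduce. The check is date arithmetic.

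**Inputs from the documents**
- Required contraception: 16 weeks = 16 × 7 = 112 days (section 5, exclusion 10).
- Planned dosing: 16 weeks, once daily = 112 doses (Synopsis; section 6).
- Last dose: the call is at week 20 and 4 weeks after the last dose, so 20 − 4 = week 16 (section 4). This agrees with the Synopsis.
- Exposure window after dosing: at least 6 half-lives (section 7, Pregnancy).

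**Assumption.** The documents give no half-life, so 3, 12 and 24 hours are used only to show a range:
- 6 × 3 h = 18 h = 0.75 day
- 6 × 12 h = 72 h = 3 days
- 6 × 24 h = 144 h = 6 days

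**Cover after the last dose.** The documents do not say whether the first tablet is taken on the day of visit 1 or the next morning, so both counts are shown for a participant on schedule.
- Count 1: contraception and dosing start on the same day. The last of 112 daily doses falls 111 days after the first, and contraception ends at day 112. Cover = 112 − 111 = 1 day.
- Count 2: the contraception clock starts at visit 1 (day 0) and the first dose is on day 1. The last dose is on day 112 and contraception ends at day 112. Cover = 112 − 112 = 0 days.

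**Uncovered interval** = max(0, 6 × half-life − cover)

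| Assumed half-life | 6 half-lives | Count 1 (cover 1 day) | Count 2 (cover 0 days) |
|---|---|---|---|
| 3 h | 0.75 day | 0 (0.75 − 1 = −0.25) | 0.75 day |
| 12 h | 3 days | 2 days | 3 days |
| 24 h | 6 days | 5 days | 6 days |

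Under count 1 a gap exists only if the half-life exceeds 24 h ÷ 6 = 4 h.

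**Early stopping.** At 24 h the gap disappears if the last dose falls at least 6 days before contraception ends. That means stopping 6 − 1 = 5 days ahead of plan under count 1, or 6 days ahead under count 2.

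**Cover if contraception ran to the week-20 call.** (20 − 16) × 7 = 28 days after the last dose. This spans 6 half-lives for any half-life up to 28 ÷ 6 ≈ 4.7 days.

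**The case against.** The best opposing case has five parts.

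- **The benchmark is borrowed.** The Pregnancy section governs stopping the product, follow-up and notification. A cautious reporting window need not equal the contraception period. This stands: a reader might infer that the two sections contradict each other, and they do not. What remains is that the protocol itself names a post-dose exposure interval and its only visible contraception requirement hardly reaches into it.
- **There may be no gap.** A reader might infer that exclusion 10 gives no post-dose cover at all. Count 1 leaves about one day, which is enough at a 3-hour half-life. This also stands and sets the lower end of the range at nil.
- **Exclusion 10 is a willingness test at entry.** It does not tell anyone to stop contraception at week 16, and fuller instructions may be in the consent pages, which were removed before review. So nothing can be inferred about what participants are told. The point is confined to the criterion as written.
- **The duration could be read to include the week-20 call.** The criterion gives the number 16, and the Study Design Overview uses the same number for the study. If week 20 was meant, the same line needs correcting.
- **Few women are affected, for days at most.** Eligible ages are 30 to 70, all participants have cardiovascular disease or proteinuria, and one of the three arms takes only placebo. This is fair and keeps the point minor.

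A further tempting reading is that the ±6-day visit window lets dosing run to 112 + 6 = 118 days, leaving days of dosing itself uncovered. The documents do not say that dosing continues to a late visit, so this is not claimed.

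**Conclusion.** The point holds as a minor drafting gap in safety cover. For an on-schedule completer, exclusion 10 gives about 0 to 1 day of contraception after the last dose, against an exposure window of at least 6 half-lives. With half-lives assumed between 3 and 24 hours, the uncovered interval is 0 to 6 days. The upper end depends on the 24-hour assumption and on a first dose the morning after visit 1; neither is stated in the documents.

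The point applies only to women of child-bearing potential among the 45 to be enrolled, whose number is not given. It has no effect on sample size, power or analysis. It is worth considering but does not show a design error.

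**What to change.** Reword exclusion 10 so that women of child-bearing potential must be willing to use contraception from entry until the existing week-20 call, defined as 4 weeks after the actual last dose. The alternative end point is at least 6 half-lives of the longer-lived product after the actual last dose. Either wording follows the participant's real dosing rather than the calendar. The week-20 version is simpler because it needs no half-life in the text. Then check that the participant instructions match.

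The cost is one line in the eligibility criteria plus that check, with no new visit or procedure. The downside is more contraception: up to about 28 extra days with the week-20 end point, or about 0 to 6 extra days with the half-life end point under the assumed range.
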